3.7 Dose Modifications

Suspected adverse reactions (SAR) (for definition see [Section 6.1.2](#)) associated with APX005M and nivolumab exposure may represent an immunologic etiology. These AEs may occur shortly after the administration of investigational products or several months after the last dose of investigational product. Management of suspected adverse drug reactions may require treatment hold, dose reduction of APX005M, or discontinuation of one of both investigational products as per [Table 4](#). If a subject experiences several toxicities, the recommended dose modification should be based on the highest grade toxicity.

See [Section 3.4.1.2](#) for supportive care guidelines, including use of corticosteroids.

Table 4: Dose Modification Guidelines for Suspected Adverse Reactions

Toxicity	Grade	APX005M	Nivolumab
Neutropenia (± febrile)	3-4	Hold	Hold
Thrombocytopenia	3	Hold. Dose reduction if > 7 days	Hold
	4	Hold. Dose reduction	Hold. Discontinue if > 7 days
	3-4 with bleeding	Discontinue	Discontinue
Diarrhea/colitis	2	1 st occurrence: hold 2 nd occurrence: dose reduction	Hold
	3	1 st occurrence: dose reduction 2 nd occurrence: discontinue	Discontinue
	4	Discontinue	Discontinue
Uveitis, eye pain or blurred vision that does not improve to Grade 1 before next cycle	2-4	Hold	Discontinue
Increased bilirubin	2	Hold	Hold
	3-4	Discontinue	Discontinue
Increased AST, ALT	2	Hold	Hold
	3	Hold. Dose reduction For subjects with liver metastasis reduce dose only if Grade 3 > 72 hours	Discontinue
	4	Discontinue	Discontinue
Endocrinopathies	2	Hold	Hold
	3-4	1 st occurrence: Hold. Institute endocrine replacement therapy 2 nd occurrence: discontinue after consultation with Medical Monitor	1 st occurrence: Hold. Institute endocrine replacement therapy* 2 nd occurrence: discontinue after consultation with Medical Monitor
Nivolumab infusion reaction	2	Administer additional premedication. Increase infusion time to 90 min	1 st occurrence: continue 2 nd occurrence: discontinue
	3	Hold for 1 cycle. Continue single agent at following cycle	Discontinue
	4	Discontinue	Discontinue

Toxicity	Grade	APX005M	Nivolumab
APX005M infusion reaction/cytokine release syndrome	3	Hold. Dose reduction	Hold
	4	Discontinue	Discontinue
Pneumonitis	2	1st occurrence: hold 2nd occurrence: discontinue	1st occurrence: hold 2nd occurrence or if > 14 days: discontinue
	3-4	Discontinue	Discontinue
Creatinine elevation	2	Hold	Hold. Discontinue if > 7 days
	3	Hold	Hold. Discontinue if > 7 days
	4	Discontinue	Discontinue
Rash or other skin toxicity	2	Hold	Continue. Hold if > 7- 14 days
	3	Hold	Hold
	4	Discontinue	Discontinue
Neurological toxicity	2	Continue	Hold
	3-4	Hold	Discontinue
Hypotension, severe dehydration, shock out of proportion to current illness or suspected adrenal crisis	3	Hold. Dose reduction	Hold
	4	Discontinue	Discontinue
Fatigue	2 >6 weeks 3	Dose reduction	Grade 2: continue Grade 3: hold
Myocarditis	2	Hold	Hold
	3-4	Discontinue	Discontinue
All other drug-related non-hematologic toxicity	3 or Severe	1st occurrence: hold 2nd occurrence: dose reduction	Hold
	4	Discontinue [#]	Discontinue [#]
Hold = hold until retreatment criteria are met (Section 3.6) Dose reduction = reduce dose by one dose level in following cycle (Section 3.7) Discontinue = permanently discontinue that investigational product * Adrenal insufficiency requires discontinuation of nivolumab regardless of control with hormone replacement # Subjects may continue treatment for transient Grade 4 toxicity (such as electrolyte imbalances ≤ 72h, amylase or lipase increase) not associated with clinical sequelae after discussion with the Apexigen Medical Monitor (or designee).			

Dose reductions for APX005M are defined in [Table 5](#). Subjects requiring more than 2 dose reductions or a dose reduction below DL1, must discontinue APX005M.

Table 5: Modified DLs for APX005M Following Qualifying Suspected Adverse Reactions

Dose Level (mg/kg)	DL1 (0.03)	DL2 (0.1)	DL2a (0.2)	DL3 (0.3)
First Dose Reduction	Discontinue	0.06	0.1	0.2
Second Dose Reduction	Not applicable	0.03	0.06	0.1

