3.6 Retreatment Criteria

Subjects that do not meet any of the criteria for treatment discontinuation ([Section 4.1](#)) may start a new cycle of APX005M and nivolumab as scheduled if WBC $>1,500/\text{mm}^3$, ANC $>1,000/\text{mm}^3$, platelets $>100,000/\text{mm}^3$, hemoglobin ≥ 8 g/dL, and disease or treatment-related AE has resolved to baseline or \leq Grade 1 (excluding Grade 2 alopecia and Grade 2 fatigue).

Subjects who have experienced a \leq Grade 2 skin suspected adverse reaction may resume treatment in the presence of Grade 2 skin toxicity.

Drug-related pulmonary toxicity, diarrhea or colitis must have resolved to baseline before treatment is resumed. Subjects with persistent Grade 1 pneumonitis after completion of a steroid taper over at least 1 month may be eligible for retreatment if discussed with and approved by Apexigen Medical Monitor (or designee).

For subjects requiring corticosteroid treatment, allow for a minimum of 7 days from last dose before beginning a new cycle.

If a subject fails to meet criteria for retreatment then the treatment cycle should be delayed and the subject should be re-evaluated weekly.

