4.1 Discontinuation of Subjects from Treatment

Subjects MUST discontinue receiving investigational product for any of the following reasons:

- Disease progression by RECIST 1.1, or disease progression following treatment beyond progression ([Section 4.1.1](#))
- Death
- Toxicity requiring discontinuation of both investigational products as outlined in the dose modification guidelines ([Section 3.7](#))
- Failure to recover from a disease or treatment-related AE to baseline or \leq Grade 1 within 12 weeks of last dose of investigational product (except Grade 2 alopecia and Grade 2 fatigue), unless the subject is benefiting from therapy and after discussion with and approval by Apexigen Medical Monitor (or designee)
- Failure to recover within 4 weeks of last dose of investigational product if AE is related to infusion reaction/cytokine release
- Inability to reduce corticosteroid to 10 mg or less of prednisone or equivalent per day within 12 weeks of last dose of investigational product and after discussion with and approval by Apexigen Medical Monitor (or designee)
- Subject's decision to withdraw for any reason from study treatment (subject withdraws consent)
- Pregnancy
- Any clinical AE, laboratory abnormality or coincident illness which, in the opinion of the Investigator, indicates that continued participation in the study is not in the best interest of the subject
- Requirement for alternative therapy
- Noncompliance with study procedures, including use of prohibited medications
- Subject is lost to follow-up
- Loss of ability to freely provide consent through imprisonment or involuntarily incarceration for treatment of either a psychiatric or physical (e.g., infectious disease) illness
- Study termination by Apexigen

The primary reason for treatment discontinuation will be documented in the eCRF.

Apexigen (or designee) must be notified within 24 hours if a subject is withdrawn from treatment.

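### Section 3.7 lets the highest-grade toxicity decide the dose action, and in at least 9 Table 4 row pairs this turns a permanent nivolumab stop into a hold

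*Protocol*

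**What the plan says.** Protocol Section 3.7 says that managing suspected adverse reactions may call for a hold, an APX005M dose reduction, or discontinuation of one or both products according to Table 4. It then adds the rule for more than one event: "If a subject experiences several toxicities, the recommended dose modification should be based on the highest grade toxicity".

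Table 4 sets actions by toxicity and grade, with a separate column for each product. Its notes define the terms: "Discontinue = permanently discontinue that investigational product" and "Dose reduction = reduce dose by one dose level in following cycle". A hold lasts until the Section 3.6 criteria are met.

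The entries that matter here are:

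- **Nivolumab is only held at Grade 4.** Neutropenia Grade 3-4 is a hold for both products. Thrombocytopenia Grade 4 without bleeding is, for nivolumab, "Hold. Discontinue if > 7 days". A first endocrinopathy of Grade 3-4 is a hold with hormone replacement, except that "Adrenal insufficiency requires discontinuation of nivolumab regardless of control with hormone replacement".
- **Nivolumab is stopped at Grade 3 and APX005M is not.** These rows are a first Grade 3 diarrhea/colitis (APX005M reduced), Grade 3 AST/ALT (APX005M held and reduced, with the rider "For subjects with liver metastasis reduce dose only if Grade 3 > 72 hours") and Grade 3 neurological toxicity (APX005M held).

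Under Section 3.6, subjects who meet no Section 4.1 criterion "may start a new cycle of APX005M and nivolumab as scheduled" once counts and adverse events have recovered. The Section 4.1 entry on Table 4 toxicity reads "Toxicity requiring discontinuation of both investigational products as outlined in the dose modification guidelines".

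**The concern.** A highest-grade rule assumes that a higher grade never carries a milder action than a lower grade of another toxicity. Table 4 breaks that assumption, because its actions reflect the kind of toxicity as well as the grade. Consider a subject with Grade 4 neutropenia and Grade 3 AST/ALT elevation. The sentence selects the neutropenia row, which holds nivolumab. The AST/ALT row would stop it permanently.

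A site that follows the sentence as written could therefore give nivolumab again after a Grade 3 hepatic, colitis or neurological event for which the protocol's own table ends nivolumab. The error is in the unsafe direction. It concerns subject safety and consistency between sites. It does not touch the ORR analysis or the Simon boundaries.

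**Working it through.** The plan gives no figure on this point, so the check is a count of Table 4 entries.

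**Coding.** Each toxicity, grade and occurrence is one cell, with its actions (hold, reduce, discontinue) recorded for each product. Bleeding and non-bleeding thrombocytopenia are separate cells. Duration riders are taken as not met. This gives 54 cells, or 47 if second occurrences are left out.

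**Pairs.** Pairing cells from different toxicities gives 906 pairs of unequal grade and 459 of equal grade, 1,365 in all. On first occurrences alone there are 684 unequal-grade pairs and 353 equal-grade pairs.

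**Conflicts.** A conflict is an unequal-grade pair in which the lower-grade cell stops nivolumab but not APX005M, while the higher-grade cell does not stop nivolumab. There are 41:

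- 16 have uveitis as the lower-grade event.
- 16 have a nivolumab infusion reaction as the lower-grade event.
- 9 have colitis, AST/ALT or neurological toxicity at Grade 3 (16 + 16 + 9 = 41).

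The uveitis and infusion-reaction pairs are set aside because timing makes them weaker. The uveitis row applies only if the event has not improved by the next cycle, and an infusion reaction is dealt with around the infusion. The remaining 9 are:

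| Grade 4 event (nivolumab held) | Condition | First Grade 3 colitis | Grade 3 AST/ALT | Grade 3 neurological |
|---|---|---|---|---|
| Neutropenia | none | stop lost; APX005M reduction lost | stop lost; APX005M reduction lost* | stop lost |
| Thrombocytopenia, no bleeding | 7 days or less | stop lost | stop lost | stop lost |
| First endocrinopathy | not adrenal insufficiency | stop lost; APX005M reduction lost | stop lost; APX005M reduction lost* | stop lost |

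*Subject to the liver-metastasis rider.

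The thrombocytopenia row already reduces APX005M, so no reduction is lost there. A reduction is lost in 4 of the 9 pairs.

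**Size.** 9/906 = 1.0% of unequal-grade pairs, or 9/684 = 1.3% on first occurrences. These are shares of table entries, not risks to subjects. The count is 9 if both conditions in the table hold, 6 if one fails and 3 if both fail.

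**Do other sections repair it?** The Section 4.1 toxicity entry covers stops of both products, whereas these three Grade 3 rows stop nivolumab alone. Section 3.6 refers back to 4.1 and speaks of restarting both products. Neither section, nor any Table 4 note, says that the most restrictive action applies or that each product is judged separately.

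**Ties.** The sentence also gives no answer when grades are equal, for example Grade 3 cytokine release syndrome (nivolumab held) with Grade 3 AST/ALT (nivolumab stopped).

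**The case against.** **The count depends on a convention.** This is true. Counting printed rows, and including uveitis and rows that stop both products, gives 15 pairs with unconditional actions, or 33 once conditional holds are added. Counting only rows whose printed grades do not overlap gives 3, all conditional. The 9 is a narrow subset under the rule stated above, so *at least 9* is the right description.

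**Reading each row separately removes the problem.** The sentence before the rule sends decisions to Table 4, and Table 4 defines discontinuation as permanent. If Section 4.1 is trusted to catch both-product stops, the same row-by-row reading would catch these. An investigator reading that way does reach the right action. But the only sentence written for several toxicities tells them to read otherwise. If 4.1 inherits that sentence, the both-product stops are exposed too and 9 is an undercount.

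**The time window is narrow.** If the Grade 3 event came first, nivolumab has already been stopped. If the Grade 4 event clears first while the other is still Grade 3, the Grade 3 row takes over. Read moment by moment, the Grade 3 event must begin and settle while the Grade 4 event persists, and within 7 days in the thrombocytopenia pairs. This reduces the frequency. The protocol does not say at what moment the rule is applied, so a site could equally compare the worst grades when planning the next cycle.

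**Safeguards exist.** The wording is advisory and Table 4 is titled as guidelines. Section 3.6 requires recovery and 7 days off corticosteroids, and Section 4.1 lets the investigator stop treatment for any adverse event. These limit the harm. None of them makes the nivolumab stop permanent, which is what the Grade 3 rows ask for.

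**Conclusion.** The concern holds. Taken literally, the Section 3.7 sentence replaces a permanent nivolumab stop with a hold in at least 9 Table 4 row pairs. Three of these are unconditional (Grade 4 neutropenia), and 4 also lose an APX005M dose reduction.

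This rests on applying the sentence as written, on the duration riders not being met, and, for 6 of the 9, on the thrombocytopenia and endocrinopathy conditions shown above.

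No event rate can be derived. Section 1.2.3 reports one Grade 4 thrombocytopenia at 1 mg/kg of APX005M alone, above the 0.3 mg/kg maximum here. Section 2.2.2 reports reactions of Grade 2 or lower at the proposed dose levels, again without nivolumab. Such coincidences are probably uncommon, and the practical effect is limited. It should still be fixed, because a stated rule gives a less safe instruction than the table it is meant to apply.

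**What to change.** Replace the sentence in Section 3.7 with:

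*If a subject has several toxicities, apply to each investigational product separately every Table 4 action required for any toxicity present. A required discontinuation of a product always prevails. Otherwise holds and dose reductions are cumulative (hold until the Section 3.6 criteria are met, then resume at the reduced dose), together with any infusion-time or premedication instruction. If more than one toxicity requires a reduction in the same cycle, APX005M is reduced by one dose level.*

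The Table 4 notes stay in force. Section 3.6 could also state that a product permanently discontinued under Table 4 is not restarted.

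A shorter clause saying only that discontinuation prevails would settle the nivolumab point, but it would leave the lost APX005M reductions and some ties unresolved. The one-level limit is needed because both rows call for an APX005M reduction in 34 of the 1,365 pairs.

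The cost is one sentence by amendment, with the IRB/IEC approval that Section 8.1.2 requires before implementation, and possibly a few more nivolumab discontinuations. It adds no subjects, procedures or analyses.

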3.8 Duration of Treatment

Subjects may continue to receive APX005M and nivolumab until any of the criteria in [Section 4.1](#) are met.

Subjects with confirmed CR may continue combination therapy up to 8 cycles (24 weeks), on a case-by-case basis, after careful evaluation and Investigator discussion with the Apexigen Medical Monitor (or designee) to determine whether the risk-benefit ratio supports administration of further study drug.

4. Study Discontinuation

4.1 Discontinuation of Subjects from Treatment

Subjects MUST discontinue receiving investigational product for any of the following reasons:

- Disease progression by RECIST 1.1, or disease progression following treatment beyond progression ([Section 4.1.1](#))
- Death
- Toxicity requiring discontinuation of both investigational products as outlined in the dose modification guidelines ([Section 3.7](#))
- Failure to recover from a disease or treatment-related AE to baseline or \leq Grade 1 within 12 weeks of last dose of investigational product (except Grade 2 alopecia and Grade 2 fatigue), unless the subject is benefiting from therapy and after discussion with and approval by Apexigen Medical Monitor (or designee)
- Failure to recover within 4 weeks of last dose of investigational product if AE is related to infusion reaction/cytokine release
- Inability to reduce corticosteroid to 10 mg or less of prednisone or equivalent per day within 12 weeks of last dose of investigational product and after discussion with and approval by Apexigen Medical Monitor (or designee)
- Subject's decision to withdraw for any reason from study treatment (subject withdraws consent)
- Pregnancy
- Any clinical AE, laboratory abnormality or coincident illness which, in the opinion of the Investigator, indicates that continued participation in the study is not in the best interest of the subject
- Requirement for alternative therapy
- Noncompliance with study procedures, including use of prohibited medications
- Subject is lost to follow-up
- Loss of ability to freely provide consent through imprisonment or involuntarily incarceration for treatment of either a psychiatric or physical (e.g., infectious disease) illness
- Study termination by Apexigen

The primary reason for treatment discontinuation will be documented in the eCRF.

Apexigen (or designee) must be notified within 24 hours if a subject is withdrawn from treatment.

4.1.1 Treatment Beyond Progression

Accumulating evidence indicates that patients with solid tumors treated with immunotherapy may derive clinical benefit despite initial evidence of progressive disease. Subjects will be permitted to continue on treatment beyond initial RECIST 1.1-defined progressive disease as long as they meet the following criteria:

- Investigator-assessed clinical benefit, without rapid disease progression, or with disease progression based primarily on changes in lymph nodes appearance Subject continues to meet retreatment criteria
- Subject tolerates study drug
- Subject has stable ECOG performance status
- Treatment beyond progression will not delay an imminent intervention to prevent serious complications of disease progression (e.g., central nervous system metastases).

The assessment of clinical benefit should take into account whether the subject is clinically deteriorating and unlikely to receive further benefit from continued treatment. All decisions to continue treatment beyond initial progression must be discussed with the Apexigen Medical Monitor (or designee), and an assessment of the risk/benefit of continuing with study therapy must be documented in the study records.

For subjects who stay on treatment beyond RECIST 1.1-defined progressive disease, all study procedures ([Section 5](#)) should be performed continuously, including tumor assessments as described in [Section 5.5](#).

Subjects will be discontinued from the treatment upon further evidence of disease progression, defined as a further increase in tumor burden as evidenced (as applicable) by a ≥ 5 mm increase in sum of measures of target or new target lesions, further increase in non-target or new non-target lesions, or an increase in the number of new lesions, as described in the iRECIST guidelines by Seymour et al [\[31\]](#).

4.2 Discontinuation of Subjects from Study

Subjects who are withdrawn from both investigational products will enter the follow-up period unless treatment discontinuation is due to any of the following:

- Subject death
- Withdrawal of consent for all study procedures
- Initiation of any anticancer therapy
- Subject is lost to follow-up
- Study termination by Apexigen

For all subjects receiving investigational products, the subsequent anticancer therapy will be documented and response to that therapy, if possible. Once this information is collected, a subject is considered off-study.

4.3 Study Termination

Apexigen has the right to terminate this study or a study site from participating in a study at any time.

Reasons for terminating the study at a specific study site may include, but are not limited to, the following:

- Subject enrollment is unsatisfactory
- Data recording is inaccurate or incomplete
- Investigator does not adhere to the protocol or applicable regulatory requirements in conducting the study

Reasons for terminating the study overall may include, but are not limited to, the following:

- The incidence or severity of AEs in this or other APX005M studies indicates a potential health hazard to subjects
- All subjects enrolled in the study have withdrawn from treatment, completed participation in the study, or are lost to follow-up.

5. Treatment Study Assessments and Procedures

5.1 Time and Events Schedule

Phase 1b Dose-escalation	Screening Phase (within 21 days prior to C1D1)	Treatment Phase									EOT (approx. 21 days after last treatment)	Follow- up
		Cycles 1 & 2					Cycles 3+					
Procedure	Day	1	2	3	8	15	1	8	2 nd Biopsy			
Written Informed Consent	X											
Inclusion/Exclusion Criteria	X	X										
Demographics	X											
Medical History	X											
Physical Examination	X	X					X				X	
Height	X											
Weight	X	X									X	
Vital Signs ^a	X	X	X	X	X	X	X	X			X	
12-lead ECG	X											
Urinalysis	X											
ECOG Performance Status	X	X					X				X	
Serum Chemistry ^b	X	X	X	X	X	X	X	X			X	
Thyroid Function Tests ^b	X						X					
Hematology Tests ^b	X	X	X	X	X	X	X	X			X	
Coagulation ^b	X	X			X	X	X	X			X	
PK Blood Tests ^c		X	X	X	X		X					
Immune PDn ^d		X	X	X	X		X	X	X		X	
Cytokines ^e		X	X	X	X		X	X	X		X	
AEs and ConMeds		X	X	X	X	X	X	X			X	X
Dosing Nivolumab		X					X					
Dosing APX005M		X					X					
Tumor Assessment ^f	X						X					X
Archived or Fresh Tumor Submission ^g	X											
Fresh Tumor Biopsy ^h	X								X			
ADA ⁱ		X					X				X	
Pregnancy Test (if applicable) ^j	X						X ^j					
Date of PD and Subsequent Therapy												X

Abbreviations: ADA = anti-drug antibodies; AE = adverse event; APTT = activated partial thromboplastin time; C1D1 = Cycle 1 Day 1; ConMeds = concomitant medications; ECG = electrocardiogram; ECOG = Eastern Cooperative Oncology Group; EOT = end of treatment; ICF = informed consent form; INR = international normalized ratio; PD = progressive disease/disease progression; PDn = pharmacodynamics; PK = pharmacokinetics; PT = prothrombin time; WOCBP = women of childbearing potential.

- ^a Vital signs: Vital signs measured within 30 min prior to nivolumab dose and at the end of the infusion, within 30 min prior to APX005M dose, end of the infusion, and 2 & 4 hours after infusion. All time points are \pm 30 min
- ^b Serum chemistry, hematology and coagulation tests performed at the local laboratory. Thyroid function tests performed every other cycle starting with Cycle 3
- ^c Blood samples for PK analyses collected in Cycles 1 and 2 before APX005M administration and at end of infusion, 4, 24 (Day 2), 48 (Day 3), and 168 hours (Day 8) from start of the infusion in that cycle. In addition, predose and end of infusion blood samples on Cycles 3 and 4 will be collected
- ^d Blood samples for immune PDn collected in Cycles 1 and 2 before APX005M administration, and 24 (Day 2), 48 (Day 3), and 168 hours (Day 8) from the start of the infusion in that cycle, in Cycles 3 and 4 before APX005M administration and 168 hours (Day 8), time of second biopsy (if applicable) and at the EOT visit
- ^e Blood samples for cytokines collected in Cycles 1 and 2 before APX005M administration, end of infusion, 4, 24 (Day 2), 48 (Day 3), and 168 hours (Day 8) from the start of the infusion in that cycle, in Cycles 3 and 4 before APX005M administration and 168 hours (Day 8), time of second biopsy (if applicable) and at the EOT visit
- ^f Tumor assessment: will be performed within 21 days prior to start of investigational products and during Treatment Phase every 8 weeks \pm 1 week. For subjects who discontinue treatment without documented PD, every effort should be made to continue monitoring their disease status by tumor imaging using the same schedule used while on treatment
- ^g Archived or fresh tumor block or minimum 12 unstained slides with tumor tissue should be obtained. Provision of archived or fresh tumor tissue for analysis is dependent upon the subject's eligibility and signing the designated ICFs
- ^h Fresh tumor core biopsies will be collected from consenting subjects prior to start of investigational products and prior to 1st scheduled tumor assessment. Selection of tumor lesions should not affect tumor assessment when feasible
- ⁱ Blood samples for anti-APX005M antibodies will be collected before dosing on Cycles 1, 2, 3, 4, and at the EOT visit
- ^j In WOCBP only, serum pregnancy test to be done within 7 days followed by a urine pregnancy test within 3 days of first dose of investigational product, or serum pregnancy test to be done within 3 days prior to first dose of investigational product. Pregnancy testing should be conducted every other cycle

Phase 2 Dose-expansion Day Procedure	Screening Phase (within 21 days prior to C1D1)	Treatment Phase			EOT (approx. 21 days after last treatment)	Follow- Up
		1	8	2 nd Biopsy		
Written Informed Consent	X					
Inclusion/Exclusion Criteria	X					
Demographics	X					
Medical History	X					
Physical Examination	X	X			X	
Height	X					
Weight	X				X	
Vital Signs ^a	X	X	X		X	
12-lead ECG	X					
Urinalysis	X					
ECOG Performance Status	X	X			X	
Serum Chemistry ^b	X	X	X		X	
Thyroid Function Tests ^b	X	X ^b				
Hematology Tests ^b	X	X	X		X	
Coagulation ^b	X	X	X		X	
Immune PDn ^c		X	X	X	X	
Cytokines ^c		X	X	X	X	
AEs and ConMeds		X	X		X	X
Dosing Nivolumab		X				
Dosing APX005M		X				
Tumor Assessment ^d	X					X
Archived or Fresh Tumor Submission (baseline) ^e	X					
Optional Paired Fresh Tumor Biopsy ^f	X			X		
PK Blood Tests ^g		X				
ADA ^h		X			X	
Pregnancy Test (if applicable) ⁱ	X	X ⁱ				
Date of PD and Subsequent Therapy						X

Abbreviations: ADA = anti-drug antibodies; AE = adverse event; APTT = activated partial thromboplastin time; C1D1 = Cycle 1 Day 1; ConMeds = concomitant medications; ECG = electrocardiogram; ECOG = Eastern Cooperative Oncology Group; EOT = end of treatment; ICF = informed consent form; INR = international normalized ratio; PD = progressive disease/disease progression; PDn = pharmacodynamics; PK = pharmacokinetics; PT = prothrombin time; WOCBP = women of childbearing potential.

^a Vital signs: Vital signs measured within 30 min prior to nivolumab dose and at the end of the infusion, within 30 min prior to APX005M dose and at the end of the infusion. All time points are ± 30min

^b Serum chemistry, hematology and coagulation tests performed at the local laboratory, within 24-48 hours of day 1 for each cycle. Thyroid function tests performed every other cycle starting with cycle 3. INR only required at

screening and as clinically indicated thereafter. D-dimer test should be performed if available at local lab at baseline and on Day 8 in Cycles 1 and 2 and as clinically indicated thereafter.

- c Blood samples for immune PDn and cytokines collected in Cycles 1 and 2 before APX005M administration, 168 hours (Day 8) from the start of the infusion in that cycle, Cycle 3 Day 1, time of second biopsy (if applicable) and at the EOT visit. Additional blood samples for cytokines collected in cycles 1 and 2 at the end of infusion and 4 hours after the start of infusion and for TCR/BCR on Cycle 3 preinfusion
- d Tumor assessment: will be performed within 21 days prior to start of investigational products and during Treatment Phase every 8 weeks \pm 1 week. For subjects who discontinue treatment without documented PD, every effort should be made to continue monitoring their disease status by tumor imaging using the same schedule used while on treatment
- e Archived or fresh tumor block or minimum 12 unstained slides with tumor tissue should be obtained for baseline analysis. Provision of archived or fresh tumor tissue for analysis is dependent upon the subject's eligibility and signing the ICF.
- f Optional fresh paired tumor core biopsies will be collected from consenting subjects prior to start of investigational products and prior to 1st scheduled tumor assessment. The biopsy should not interfere with the RECIST 1.1 tumor assessment. .
- g Blood samples for PK analyses collected every 3rd cycle (i.e., Cycles 1, 3, 6, 9, 12, etc) at predose and at end of infusion
- h Blood samples for anti-APX005M antibodies will be collected before dosing every 3rd cycle (i.e., Cycles 1, 3, 6, 9, 12, etc) and at the EOT visit
- i In WOCBP only, serum pregnancy test to be done within 7 days followed by a urine pregnancy test within 3 days of first dose of investigational product, or serum pregnancy test to be done within 3 days prior to first dose of investigational product. Pregnancy testing should be conducted every other cycle

